will be counseled to modify their diet, if necessary, to correct the abnormality, or withdrawn from the study at the PI's discretion for safety. Risk of hypoglycemia will be minimized by excluding participants with history of being hospitalized for a glycemic event 12 months preceding study enrollment and with A1C >10. In addition, participants who are on insulin and insulin secretagogues will be required to have the permission of their diabetes provider to participate in the study and their diabetes provider will agree to adjust their medications, if indicated, during the study. Risk of loss of confidentiality will be minimized by ensuring the physical privacy of participants during face-to-face interviews, discussing expectations of confidentiality with all group participants, and storing research documents in a secured area accessible only to the study staff. All staff will be trained regarding these procedures.

Potential benefits: (Phase 2 participants only)

- Improved blood pressure
- Reduced CVD risk
- Improved blood glucose
- Improved lipids
- Contribute to health-related knowledge that may serve to benefit patients with CKD in the future (Phase 1 and Phase 2 participants)
- Alternatives to participating: (Phase 2 participants only) - pharmacologic and non-pharmacologic strategies to control hypertension and CKD as recommended by patients' healthcare provider.

Importance of the knowledge expected to result from the research: Phase 1 - knowledge generated from focus groups will inform the design of the culturally-sensitive and disease-relevant diet counseling intervention that will be delivered in Phase 2. Phase 2 - knowledge will determine the preliminary effectiveness and safety of DASH diet counseling to lower BP among Blacks with CKD.

Data Analysis & Statistical Considerations

Phase 1 analytic strategy

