To evaluate preliminary efficacy of our counseling intervention on DASH adherence, BP, and potassium, we will repeat 24-hour diet recalls, 24-hour urine biomarker studies, office BP, 24-hour ABP, and clinical laboratory studies for all study participants at weeks 12 (post-intervention; primary endpoint) and 24 (after a 3-month post-study observation period; exploratory endpoint). We anticipate that active arm participants will exhibit greater improvement in DASH adherence and a larger reduction in 24-hour mean SBP. Initial summary statistics and graphical displays will be used to make reasonable outcome distribution assumptions. Using an intention to treat, primary analyses to compare the amount of change over time and trajectories of change between the two study arms in DASH diet score, 24-hour mean SBP, and serum potassium will use generalized linear mixed models, with a random effect to capture longitudinal within-person correlation. The primary model for BP outcomes will include study arm, time point, and their interactions, consistent with the randomized trial. Subsequently, a secondary model will be refit to adjust for age, gender, race baseline daily sodium intake, and time-specific values of eGFR, weight, and hypertension medication indicator. Exploratory outcomes in office SBP and DBP, 24-hour DBP, 24-hour urine biomarkers of diet adherence (potassium, phosphorus, urea, and sodium), and additional CKD-relevant metabolic markers (serum phosphorus and bicarbonate) will be assessed using the same analytic strategy. Our analytic approach can be used with any distribution within the exponential family (e.g., normal, binomial, Poisson, and skewed distributions such as gamma and lognormal). The decision on which is most appropriate will be made using initial summary statistics and graphs. The exponential family is broad enough that further transformations of the data are not expected to be necessary, but if so, we will use historically-common transformations to approximate normality. The proportion of participants who do and do not meet safety thresholds (serum potassium >5.2 mg/dl per testing lab standards, phosphorus >5.5 mg/dl, bicarbonate <18 mmol/L) in the two study arms will be compared using the same longitudinal generalized linear mixed model approach, assuming the Binomial distribution.

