Unlike a large clinical trial, our pilot study will not have statistical power to establish the effectiveness and safety of DASH in this population. However, this initial pilot study will generate critical evidence for estimating effect sizes and showing feasibility of the intervention, that will guide future work. Power:

Our power estimate is based on the primary aim comparing treatment arms on the SBP measure. Assuming a 20% attrition rate of 5 per group and using two-sided tests at a type I error rate of 5%, a final sample size of 20 per group will give us 80% power to detect a 7.7 mmHg difference in the change in SBP at 12 weeks between groups, assuming a within-person correlation of 0.7 over time and a standard deviation of SBP of 11 mmHg. A between-group difference of 11.4 and 7.8 mmHg were observed in prior DASH feeding and counseling intervention studies. To assess the sensitivity of the results to any missingness in the data, we will use multiple imputation to create complete cases while incorporating the uncertainty in doing so in the assessment of model parameters. The SAS/STAT software, version 15.1 for Windows and R packages (version 3.6.1) will be used for the data analyses, after extraction from the research database REDCap (Research Electronic Data Capture).

Phase 2c: For this qualitative aim, self-reported barriers and facilitators to DASH diet adherence among active arm participants will be described. Interview transcripts will be analyzed using framework analysis. A thematic analysis approach will be used to allow new concepts to emerge inductively from the data.

Data & Safety Monitoring

Safety monitoring:

Hyperkalemia: Hyperkalemia is the most serious potential risk that CKD patients who follow the DASH diet may experience. Therefore, we plan to actively monitor serum potassium concentrations during the intervention and intensify monitoring during periods that elevations in potassium, if they occur, would most likely be observed. When and how frequently we plan to measure serum potassium has been determined by:

- when participants will be counseled about potassium-rich and potassium-poor foods by the dietitian (i.e., week 2-3);
- knowledge about timing of steady-state concentrations of potassium following increased oral intake; and

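### The only sensitivity analysis for missing data is multiple imputation with no stated departure from missing at random, so for dropout before week 12 it would largely repeat the primary estimate

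*Combined protocol and SAP*

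**What the plan says.** The missing-data provision is in the Power paragraph of Data Analysis & Statistical Considerations: "To assess the sensitivity of the results to any missingness in the data, we will use multiple imputation to create complete cases". The rest of that sentence adds only that the imputation's own uncertainty will be carried through to the estimates. Nothing more is said about it. No imputation variables, missingness assumption, delta shift, reference arm or tipping point is given.

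Under Phase 2b analytic strategy, the primary analyses are by intention to treat and "will use generalized linear mixed models, with a random effect to capture longitudinal within-person correlation". For blood pressure, "The primary model for BP outcomes will include study arm, time point, and their interactions". Week 12 is the primary time point. The covariate-adjusted model in that section is a second efficacy model, not a missing-data analysis. Reasons for withdrawal are reviewed under Phase 2a as part of feasibility, with no link to the efficacy analysis.

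The plan expects losses: "Assuming a 20% attrition rate of 5 per group". It also describes two routes out of the study. Under Risk/Benefit Assessment, a participant with a laboratory abnormality may be counseled on diet or "withdrawn from the study at the PI's discretion for safety". Under Data & Safety Monitoring (Study withdrawal), a hospital admission for a glycemic event leads to withdrawal.

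**The concern.** A likelihood-based mixed model handles missing outcomes by assuming that, given the data observed, an unmeasured participant would have resembled measured participants in the same arm. Standard multiple imputation draws the missing values under the same assumption. If the assumption is wrong, both analyses are wrong in the same direction and by nearly the same amount. Their agreement could then be read as robustness to dropout when it is close to built in.

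The assumption is open to doubt here. DASH participants attend 12 weekly group sessions, and one who leaves loses that counseling. Phase 2b names only weeks 12 and 24 for repeat ambulatory monitoring, so a participant who leaves earlier may contribute only a baseline ambulatory value (Table 1 is not visible in the public text). There would then be little on-treatment ambulatory data to predict from.

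What is at stake is the size of the estimated effect. The Power paragraph says that the pilot will not establish effectiveness, but that its effect sizes will guide later work.

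**Working it through.** Differences below are the extra fall in SBP in the DASH arm, in mmHg.

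**1. Inputs (Power paragraph; Design & Procedures, Aim 2).** 50 randomized 1:1, so 25 per arm; 5 lost per arm; SD 11; within-person correlation 0.7; two-sided 5%. The plan states that "a final sample size of 20 per group will give us 80% power to detect a 7.7 mmHg difference in the change in SBP".

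**2. The plan's own figure.**
- SD of change = 11 × √(2 × (1 − 0.7)) = 8.52.
- SE of the difference with 20 per arm = 8.52 × √(2/20) = 2.69.
- Power for 7.7 = 81.5% (normal) or 79.5% (noncentral t, 38 df).
- 20 / (1 − 0.20) = 25 per arm.

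The stated 80% reproduces and is not in dispute.

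**3. Effect in all randomized participants if unmeasured DASH participants gain nothing.** This is an assumed scenario. The measured participants show 7.7, and 5 of 25 DASH participants are unmeasured with zero benefit:

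0.80 × 7.7 + 0.20 × 0 = 6.16, a shortfall of 1.54.

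**4. Would the planned imputation show it?** A simulation of 400 trials used the inputs above, baseline and week 12 only, and the scenario of step 3. The likelihood estimate was computed by within-arm regression of week 12 on baseline, as a stand-in for the mixed model. The imputation used the same regression with 50 imputations.

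| Analysis | Mean difference |
|---|---|
| Full data, nobody missing | 5.95 |
| Likelihood, missing at random | 7.42 |
| Standard multiple imputation | 7.41 |

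The last two correlate at 0.998 across trials, and the SD of their difference is 0.17. Both miss the full-data value by 7.42 − 5.95 = 1.47, close to the 1.54 of step 3. All three means fall a little below their expected values (6.16 and 7.7), which is compatible with simulation noise.

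**5. How far must unmeasured DASH participants deviate?** Let delta be the amount by which they are worse than predicted, with unmeasured controls left as predicted and the SE held at 2.69.
- Estimate = 7.7 − (5/25) × delta.
- Delta 5 gives 6.7; 7.7 gives 6.16; 10 gives 5.7; 15 gives 4.7.
- Smallest significant difference (t, 38 df) = 5.45.
- Tipping point = (7.7 − 5.45) / 0.20, or about 11.2.

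It depends on the number unmeasured in the DASH arm:

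| Unmeasured of 25 | Estimate at zero benefit | Tipping delta |
|---|---|---|
| 3 | 6.8 | 18.7 |
| 5 | 6.2 | 11.2 |
| 7 | 5.5 | 8.0 |
| 10 | 4.6 | 5.6 |

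**6. Consequence for a later trial.** Suppose it is sized for 80% power at 7.7 and the effect in all randomized is 6.16. By the normal approximation, (1.960 + 0.842) × 0.8 − 1.960 = 0.28, which is power of about 61%. Restoring 80% needs (7.7 / 6.16)² = 1.56 times the sample.

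**The case against.** **Missing at random is inferred.** The documents never use the term, and imputation can be run under other assumptions. This stands: the fault is the missing specification, not the method. As written, though, nothing departs from the standard form.

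**The sentence covers all missing data, not dropout alone.** The secondary model uses time-specific eGFR, weight and a medication indicator, and imputing missing covariates there can add something real. This stands and is a reason to keep the imputation.

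**The near-perfect agreement comes from a simulation with two time points and no auxiliary variables.** The compensation section mentions week-4 assessments, and the safety section lists DASH-arm potassium at weeks 0, 2, 4, 8 and 12. Using these could separate the two analyses and make missing at random more plausible. It still would not test the assumption.

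**A reader might infer that the protocol makes withdrawal informative.** The documents support only that it can. Withdrawal after a laboratory abnormality depends on a recorded value, and may be missing at random if that value is in the model. It is also discretionary. Nothing in the text ties a glycemic admission to unmeasured SBP.

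**A reader might infer that both analyses credit every leaver with the full benefit of attenders.** They do not. Under intention to treat, a participant who stops attending but is measured at week 12 contributes the actual value, and predictions use each person's own earlier data. The concern is limited to missing outcomes.

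**A reader might infer that the DASH proportion above the potassium threshold could be wrong by 5/25 = 20 percentage points.** That is an outer bound. It ignores the interim potassium tests, and a participant withdrawn for high potassium already has a recorded high value. Counting only DASH leavers as exceeding would bias the comparison against that arm.

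**The shift is small for a pilot.** About 1.5 mmHg is well inside a 95% half-width of 5.45. That is a fair limit on severity. But this shift is a bias and the half-width is sampling error, and the estimate is meant for later planning.

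**Conclusion.** The point holds in a limited form. No analysis in the plan would show whether dropout before week 12 biases the effect estimate, because the one offered for that purpose, in its standard form, shares the primary model's assumption.

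The size is about 1.5 mmHg on a 7.7 mmHg estimate. This assumes 20% of the DASH arm unmeasured, zero benefit in them, and controls missing at random. The documents establish none of these as fact. They also record that the study was ended while Cohort 5 was being screened, so 25 per arm and 5 lost are planning figures.

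A reader might go further and conclude that a significant SBP result would rest on dropout. The plan's figures do not support that: at 5 of 25 unmeasured, significance survives the zero-benefit scenario (6.16 against 5.45) and is lost only at a shift of about 11 mmHg. It would be lost under zero benefit with 10 of 25 unmeasured (4.6), even with the SE held fixed.

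The change is worth making because it is cheap and the effect estimate is a main product of the pilot. It does not invalidate the primary analysis.

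**What to change.** Keep the multiple imputation and replace its sentence in the Power paragraph with wording such as:

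> Multiple imputation will be run by arm under missing at random, using baseline values, week-4 assessments, surveillance laboratory values (including any that prompted withdrawal), session attendance and model covariates. Two further analyses will address week-12 24-hour mean SBP that is missing in the DASH arm: (i) control-based imputation, drawing missing values from the control-arm distribution given the participant's earlier data; (ii) delta-adjusted imputation, adding 0 to at least 15 mmHg in 2.5 mmHg steps and reporting the shift at which the conclusion changes. Analysis (i) will also be applied to the DASH score. Missing outcomes and reasons for withdrawal will be reported by arm.

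The range must reach at least 15 mmHg. In the planning scenario 10 gives 5.7, still above 5.45, while 12.5 gives 7.7 − 0.20 × 12.5 = 5.2. With few missing outcomes the range must go further (18.7 with 3 of 25).

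For the potassium threshold, use the recorded surveillance and withdrawal values. If a worst-case table is shown, apply the same rule to leavers in both arms. The interim potassium schedule is stated for the DASH arm only, so say how unequal testing will be handled.

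The cost is plan wording and some code in the SAS or R already named, with no new visits or data. The downside is that a less favourable sensitivity estimate may have to be reported.

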- Hyperphosphatemia: the dairy and protein content of the DASH diet makes it a rich source of phosphorus. Urinary excretion of phosphorus is reduced in advanced kidney disease. Although unlikely, sudden, severe hyperphosphatemia, can cause hypocalcemia and result in muscle paralysis or calcium-phosphate deposition into soft tissue.
- Hypoglycemia: Although the DASH diet is not a low-carbohydrate diet (approximately 55% of daily calories from carbohydrates), individuals with type 2 diabetes mellitus who are prescribe insulin or insulin secretagogues will be at risk for developing hypoglycemia if their typical daily intake of carbohydrates is higher than the DASH diet. Hypoglycemia can cause tremor, diaphoresis, confusion, tachycardia, hunger and nausea, fatigue, headache, blurred vision, and irritability. If severe and left untreated hypoglycemia can lead to seizure, loss of consciousness, and death.
- Complications from venipuncture: Venipunctures may cause some momentary discomfort and/or bruising at the site of needle entry. Infection, excess bleeding, or clotting are also possible, although unlikely. Occasionally, blood drawing can cause dizziness, lightheadedness, nausea and/or fainting.
- Food allergy and lactose intolerance: Participants may be exposed to new foods, creating the possibility for a food allergy to be discovered resulting in an allergic reaction. In addition, they will be provided a diet that is rich in dairy, possibly leading to symptoms of lactose intolerance.
- Loss of confidentiality (Phase 1 and Phase 2 participants): Privacy in the context of this study includes confidentiality of data and personal information and in handling and reporting of data.
- Risks of serious electrolyte abnormalities will be minimized by excluding participants who have elevated serum potassium concentrations at baseline and who are at risk for developing hyperkalemia. Furthermore, surveillance labs will be drawn at pre-determined intervals during the study to assess for changes in key CKD-relevant electrolytes and minerals and participants

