- lessons learned from our DASH diet pilot feeding study in which we observe trends in serum potassium among patients with CKD stages 3a and 3b who were given the DASH diet (i.e., Black adults with CKD). Participants in the feeding study had slightly lower risk for hyperkalemia due to their higher eGFR compared to the target population (CKD stages 3b and 4) being recruited for the current study.

As outlined in our proposal, serum potassium will be measured at the following scheduled intervals for participants who are randomized to the DASH diet counseling intervention: weeks 0, 2, 4, 8, and 12. Additionally, we plan to perform reflex laboratory testing contingent on the results from scheduled testing.

Blood pressure is a primary outcome for the study and will be measured during scheduled data collection visits. The study PI will be alerted during the study visit about participants with symptomatic severe hypertension or hypotension to make timely decisions about medical referral.

Hypoglycemia: Although DASH is not a low-carbohydrate diet, participants with Type 2 Diabetes Mellitus (T2DM) may be at risk for developing hypoglycemia if the carbohydrate content of DASH is lower than their typical daily consumption and they are prescribed insulin or insulin secretagogues. Safety oversight for study procedures involving patients with T2DM will be provided by [name], who is a Duke board-certified endocrinologist who specializes in caring for patients with diabetes. Investigators will take the following precautions to minimize risks of hypoglycemia and enhance the safe participation of patients with T2DM in the study:

Agreement of participants' diabetes provider (DP) to manage blood glucose (BG) Investigators do not assume responsibility for clinical care of the participants' diabetes. Potential participants with T2DM who are prescribed insulin or an insulin secretagogue will only be allowed to participate in the study if their DP (i.e., primary care provider or endocrinology provider) approves of their participation and agrees to manage their diabetes medications during the study (see "Diabetes Provider Opt-in Contact Protocol"). Participants will be advised to maintain follow up appointments with their DP and to seek sooner follow-up if indicated for abnormal glucose values.

Blood glucose self-monitoring

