It is common practice for individuals with T2DM who are prescribed insulin to be advised by their DP to monitor their BG concentrations several times per day (e.g., at least once daily for basal insulin users, approximately 3-4 times daily for basal-bolus insulin users). Participants will be advised to continue to follow their providers' advice regarding how often they monitor their BG. Since the study population may be at heightened risk of hypoglycemia due to the presence of CKD, the study team will provide each participant with diabetes with a handout based on ADA material that reviews hypoglycemia precautions (see "Hypoglycemia (Low blood sugar)" handout) and encourage them to contact their provider to report hypoglycemia so medications may be adjusted if indicated. As a precaution, hypoglycemia will be defined as BG <80 mg/dl, instead of <70 mg/dl, given this is a higher risk population.

Assessment of baseline dietary pattern

All study participants who meet inclusion criteria will be asked to complete 2-3 dietary recalls at baseline. We will determine typical daily carbohydrate consumption for all participants with T2DM who are prescribed insulin or insulin secretagogues and are randomized to the intervention arm. We will communicate participants' typical daily carbohydrate consumption to their DPs to make them aware of how their participant's current carbohydrate amount compares to the DASH diet. This information can be used at the discretion of the DP to help triage when the patient should be seen to decide on appropriate follow up.

Study withdrawal

Individuals who require hospital admission for a glycemic event during the study period will be withdrawn from the study.

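### Hypoglycemia is a named DASH risk with its own cut-off, yet in the text available events without hospital admission go only to the outside provider and the safety analysis omits them

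*Combined protocol and SAP*

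**What the plan says.** All places are in the combined protocol and SAP.

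- **Named risk.** Risk/Benefit Assessment says that people with T2DM who are "prescribe insulin or insulin secretagogues will be at risk for developing hypoglycemia" when DASH supplies less carbohydrate than they usually eat, and it lists severe consequences. Data & Safety Monitoring gives hypoglycemia its own heading and repeats the condition that "they are prescribed insulin or insulin secretagogues".
- **Cut-off.** Blood glucose self-monitoring states: "As a precaution, hypoglycemia will be defined as BG <80 mg/dl, instead of <70 mg/dl, given this is a higher risk population".
- **Detection.** The same subsection leaves frequency to the outside provider: "Participants will be advised to continue to follow their providers' advice regarding how often they monitor their BG".
- **Reporting.** The study team is to supply a handout and "encourage them to contact their provider to report hypoglycemia so medications may be adjusted if indicated". The Hypoglycemia subsection adds: "Investigators do not assume responsibility for clinical care of the participants' diabetes".
- **Study action.** Study withdrawal removes anyone admitted to hospital for a glycemic event. Phase 2a reviews reasons for withdrawal as a feasibility item.
- **Analysis.** Phase 2b compares the arms on the proportions crossing three safety thresholds: a serum potassium limit, then "phosphorus >5.5 mg/dl, bicarbonate <18 mmol/L". No glucose measure or glycemic event is among its other outcomes.
- **Intended conclusion.** The closing paragraph of Risk/Benefit Assessment expects Phase 2 to yield preliminary knowledge of safety as well as effectiveness. The text before the power paragraph concedes that the pilot lacks power to establish either.

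**The concern.** The protocol identifies a harm, says who is exposed to it and chooses a precautionary definition. It then describes no way for an event that meets the definition to enter the study data, and no analysis that would use it. Leaving diabetes care with the participant's own provider is a legitimate choice and is not at issue. What is missing is the data route.

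At stake is what the pilot can say about safety. Its stated purpose is to guide later work. A follow-on trial planned from its safety results would have information on three laboratory markers, and none on how often at-risk participants had low glucose short of admission.

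**Working it through.** **The plan's own figure.** The documents give no figure for hypoglycemia. The only calculation to reproduce is the power for systolic pressure, which matters here only because it fixes the arm sizes.

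- SD of change = 11 × √(2 × (1 − 0.7)) = 8.52 mmHg.
- Power with 20 per arm for 7.7 mmHg = Φ(7.7 / (8.52 × √(2/20)) − 1.96) = 81.5%; with the noncentral t on 38 df, 79.5%. The plan states 80%, so the figure reproduces.
- 20 / (1 − 0.20) = 25 per arm, which matches 50 enrolled.

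**Tracing an event through the text.**

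| Step | Event without admission | Event with admission |
|---|---|---|
| Detected by | Self-monitoring as the provider advises; no study schedule or log described | Hospital |
| Reported to | Participant's own provider | Study acts by withdrawal; route not described |
| Recorded by the study | No route described | Through withdrawal |
| Analyzed as safety | No | No; reviewed as a feasibility item, low and high glucose not separated |

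Of the three thresholds compared in Phase 2b, 0 of 3 concern glucose. Data collection lists a basic metabolic panel, hemoglobin A1c and fructosamine, but none of these counts low readings between visits. Medications are collected by questionnaire, so changes in glucose drugs may be partly recoverable.

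**Is there a common place to ask?** Subject Recruitment and Compensation lists four data collection visits for both arms: baseline and weeks 4, 12 and 24. The recall windows would be 4 − 0 = 4, 12 − 4 = 8 and 24 − 12 = 12 weeks.

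**What a count could show.** After zero events in n participants, the exact two-sided 95% upper limit is 1 − 0.025^(1/n).

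| n per arm | Basis | Upper limit |
|---|---|---|
| 25 | All randomized | 13.7% |
| 20 | After planned attrition | 16.8% |
| 12 | Assumed at risk | 26.5% |
| 5 | Assumed at risk | 52.2% |

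The number on insulin or a secretagogue is not given; 5 to 12 per arm is an assumption. For a comparison, take 10 at risk per arm and event proportions of 10% and 30% (both assumed). With p̄ = 0.20, power = Φ[(0.20 − 1.96 × √(2 × 0.20 × 0.80 / 10)) / √((0.10 × 0.90 + 0.30 × 0.70) / 10)] = Φ(−0.87), about 19%. The count can be described but not usefully tested.

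**The case against.** The strongest reply has four parts.

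1. **The safety aim is narrower than a general one.** The safety hypotheses in Aim 2 concern potassium and named laboratory markers, and the plan disclaims power for safety. This stands: no stated hypothesis fails. But lack of power is no reason to leave a named risk out of a descriptive report.
2. **The cut-off is not an endpoint.** It comes directly after the handout and the advice to call the provider, so it reads naturally as an earlier prompt for that call. This also stands, and it would be wrong to infer that the cut-off has no function. What it lacks is a use in the study data.
3. **Safeguards exist.** An endocrinologist oversees study procedures for participants with T2DM, and providers of those on insulin or a secretagogue must approve participation and agree to manage their drugs. These protect participants but do not produce counts.
4. **Absence is not certain.** Table 1, the provider contact protocol and the handout are cited but are not in the text available. A capture form there cannot be excluded. Phase 2b would still omit the event.

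Two further inferences are tempting and are not supported. A reader might see a contradiction between the Hypoglycemia subsection, which puts secretagogue users at risk, and Blood glucose self-monitoring, which describes usual practice for insulin users. The first says who is at risk and the second describes common practice, then defers to each provider; neither says who must have readings. A reader might also infer that glucose drugs would be adjusted in the DASH arm only, because carbohydrate intake is sent to providers for that arm alone. The provider agreement applies to every participant on these drugs, in either arm. What may differ by arm is awareness.

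**Conclusion.** The point holds for hypoglycemia that does not lead to admission. On the text available, no such event reaches the study, and the Phase 2b safety comparison has no place for one. Admitted events would be known through withdrawal, but not as a safety outcome.

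A reader might go further and say that the trial would report zero events when some had occurred. The documents do not support that. With no hypoglycemia outcome defined, the trial would give no figure at all, which is a gap in its safety statement and not a false claim.

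The size of the gap in participants cannot be computed, because the number on insulin or a secretagogue is not stated. The conclusion rests on the text as supplied and on the assumption that the unseen attachments do not define a safety outcome. It does not touch the primary blood pressure analysis. The change should be made because it costs little and closes a gap between a named risk and the safety report.

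**What to change.** **Collect.** At the week 4, 12 and 24 visits, ask every participant with T2DM on insulin or a secretagogue, in both arms and in identical wording: any BG below the protocol's own cut-off, or any symptomatic low, since the last visit; and any change in glucose drugs. Use the existing medication questionnaire for the latter where possible. If Table 1 or the provider contact protocol already holds such a form, use it.

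**Report.** Add to Phase 2b one descriptive safety table by arm: number at risk; number with at least one event, admitted and non-admitted, with exact intervals; number with a glucose-drug change; and a note of how many self-monitor. Do not count events volunteered at the weekly DASH sessions in the between-arm figures, since controls have no matching contact.

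**Cost.** Two questions at visits already held and one table, with no extra visit and no larger sample. Recall over 4 to 12 weeks is imperfect. Awareness may be higher in the DASH arm because of the weekly sessions and the carbohydrate information sent to providers, so identical wording limits differential reporting but does not remove it. Numbers will be small and the table is descriptive only.

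Design & Procedures indicates that the study was ended while Cohort 5 was being screened. If data collection is over, tabulate what can be recovered, state in the report that hypoglycemia without admission was not systematically captured (if no form exists), and carry the questions into the follow-on trial.

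No change to the cut-off or to diabetes management is proposed.
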